### 6.1.2 Non-Quantifiable Concentrations

All concentration values reported as no results (not collected or not determined) values will be treated as missing. For the calculation of concentration summaries, all concentrations below the quantifiable limit (BLQ) will be treated as 0. For the purpose of calculating PK parameters and plotting mean and individual concentration-time profiles, BLQ values will be treated as 0 prior to the first measurable concentration. After the first measurable concentration, subsequent BLQ values (or mean concentration values that are BLQ) are treated as missing.

## 6.2 Biomarker Assessment

Collect mid-stream free-flow urine for analysis of urine exploratory biomarkers (e.g., PC1, PC2, NGAL, KIM-1, MCP-1, B2M and CLU) during Screening and Day -1 and collect serum samples during Screening and Day -1 for serum exploratory biomarkers (e.g., Cystatin-C, IGFALS, Alb, CT-pro-AVP, N-acetyl-1-methylhistidine, and others).

## 7 STATISTICAL METHODS

### 7.1 General

The statistical analysis will be conducted following the principles specified in the International Council for Harmonisation (ICH) Topic E9 Statistical Principles for Clinical Trials (CPMP/ICH/363/96).

All statistical analyses will be performed using the statistical software SAS Grid/ SAS Linux - SAS®, Version 9.4 or newer and any exceptions will be detailed in the CSR.

All results collected in the database will be presented in listings. All continuous data will be listed with the same precision as presented in the database.

Unless otherwise noted, continuous variables will be summarized descriptively using the number of non-missing observations (n), arithmetic mean (mean), standard deviation (SD), coefficient of variation (%CV), first (Q1) and third quartiles (Q3), median, minimum, and maximum; categorical variables will be summarized using the frequency count and the percentage of subjects in each category.

In the data listings, study day relative to dose of study drug will be presented. Study day relative to dose will be calculated as event date – dose date (+1 if event date  $\geq$  dose date).

Baseline will be the latest available measurement (scheduled or unscheduled assessment) prior to the study drug administration in the study.

Subjects will be analyzed based on the actual treatment received.

For numerical variables, change from baseline will be calculated as (Post baseline value – Baseline value).

For safety summaries, the unscheduled and repeat assessments will not be included in descriptive statistics; however, all results will be included in the data listings.

All data will be summarized by cohort and treatment group, pooled RGLS8429, and pooled placebo unless otherwise specified.

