2.3.7. Safety Laboratory Tests

The Safety Laboratory Tests listed in [Table 2](#): should be obtained at the times specified in the Schedule of Assessments and Procedures (see [Table 1](#)). Detailed collection, processing, storage, and shipment instructions will be provided in a Laboratory Manual.

Table 2: Safety Laboratory Tests

Hematology – Complete Blood Count	

 • Hemoglobin (Hb) • Hematocrit (Hct) • Red Blood Cell (RBC) Count • Mean Corpuscular Volume (MCV) • Mean Corpuscular Hemoglobin (MCH) • Mean Corpuscular Hemoglobin Concentration (MCHC) 	
 • Platelet Count • White Blood Cell (WBC) Count and Differential • Absolute Neutrophil Count • Absolute Lymphocyte Count • Absolute Monocyte Count • Absolute Eosinophil Count • Absolute Basophil Count
Chemistry – Metabolic Panel	

 • Glucose • Calcium • Albumin (Alb) • Total Protein • Sodium • Potassium • Bicarbonate (Total CO₂) • Chloride • Blood Urea Nitrogen (BUN) • Uric Acid • Creatine kinase (CK) 	
 • Phosphate • Lactate Dehydrogenase (LDH) • Blood Urea Nitrogen (BUN) • Creatinine (Scr) • Alkaline Phosphatase (ALP) • Alanine Aminotransferase (ALT) • Aspartate Aminotransferase (AST) • Gamma-Glutamyl Transferase (GGT) • Total Bilirubin • Direct Bilirubin
Urinalysis ^a	

 • Specific Gravity • pH • Protein • Glucose • Ketones 	
 • Blood (Hemoglobin) • Leukocyte Esterase Nitrite • Bilirubin • Urobilinogen • Microscopic Examination ^b
Coagulation	

 • International Normalized Ratio (INR) • Prothrombin Time (PT) 	
 • Activated Partial Thromboplastin Time (aPTT) • Fibrinogen
Lipids	

 • Total cholesterol • Triglycerides 	
 • High-density Lipoprotein (HDL) • Low-density Lipoprotein (LDL)

Unscheduled safety laboratory assessments may be obtained at any time during the study to assess potential safety concerns.

a Urinalysis testing will be conducted using standard commercial test strips (urine dipstick).

b Only if urine dipstick is positive for blood, protein, or leukocyte esterase nitrate.

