8. DATA ANALYSIS / STATISTICAL METHODS

8.1. General Considerations

The primary objective of this study is to assess the safety and tolerability of RGLS8429. Secondary objectives include characterizing the PK of RGLS8429 and to characterize several exploratory urine and serum biomarkers.

Tabular summaries and analysis results will be generated by dose level for RGLS8429 and placebo (pooled across all cohorts). Descriptive statistics by dose level and treatment group will be tabulated by visit. For continuous endpoints, the descriptive statistics will include the number of observations, mean, median, standard deviation, coefficient of variation (%CV), first and third quartiles, minimum and maximum. Geometric mean and geometric %CV will be presented where appropriate. For categorical endpoints, the number and percentage of subjects will be summarized by dose level and treatment group.

Details of all statistical methods will be provided in the Statistical Analysis Plan.

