8.4.3. Safety Analysis

The Safety Population will be used for all safety analyses. No formal statistical tests will be conducted to assess the safety or tolerability of RGLS8429.

Subject incidence of all TEAEs, all TEAEs related to study drug, and all SAEs will be tabulated by system organ class and preferred term. All fatal adverse events, SAEs, and TEAEs leading to withdrawal from study drug will also be listed.

The incidence of DLTs will be summarized by dose level and treatment group.

The analyses of safety laboratory tests, vital signs, and ECGs will include summary statistics over time tabulated by cohort. Similarly, changes from baseline will be summarized. Shifts based on normal ranges between the baseline and the worst on-study value will be tabulated by dose level and treatment group.

The results from the central reader assessment of ECGs extracted from the Holter data will be used in all statistical analysis. The following intervals will be summarized by treatment group: PR, QRS, RR, HR, uncorrected QT, QTcB, and QTcF. Details of additional analyses will be provided in the Statistical Analysis Plan.

The total dose of study drug and the proportion of subjects receiving each dose level will be summarized using descriptive statistics.

Changes from baseline in the SARA test scores will be summarized descriptively over time and by treatment cohort for each category and the total score. The SARA is a tool for assessing ataxia. It has eight categories with accumulative score ranging from 0 (no ataxia) to 40 (most severe ataxia). When completing the outcome measure, each category is assessed and scored accordingly. Scores for the eight items range as follows:

1. Gait (0-8 points),
2. Stance (0-6 points),
3. Sitting (0-4 points),
4. Speech disturbance (0-6 points),
5. Finger chase (0-4 points),
6. Nose-finger test (0-4 points),
7. Fast alternating hand movement (0-4 points),

8. Heel-shin slide (0-4 points).

Once each of the 8 categories has been assessed, the total is calculated to determine the severity of ataxia.

For motor activities of the four extremities (Items 5-8), assessments are performed bilaterally, and the mean values are used to obtain the total score.

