### 7.2 Handling of Dropouts or Missing Data

There will be no imputations for missing data other than that implicit by ignoring missing data when using the trapezoidal rule for the calculation of AUCs. For all variables, only the observed data from the subjects will be used in the by-visit summaries.

The following imputation dates for AE and concomitant medication will only be applied for determination of TEAEs and prior/concomitant medication.

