### **7.17.2 Clinical Laboratory Assessments**

Clinical laboratory data will be summarized using System International (SI) units and the Safety Population will be used.

Observed and change from baseline of continuous clinical laboratory values (serum chemistry, coagulation panel, hematology, lipids, and urinalysis) will be summarized for each parameter at each visit/timepoints using descriptive statistics.

Shift from baseline to worst post-baseline laboratory findings based on normal range criteria will also be summarized.

A listing of all clinical laboratory data for each subject at each visit will be presented. Laboratory values outside the reference range will be flagged with 'L' for low and 'H' for high in the data listings and a list of abnormal values will be presented.

For female subjects, serum/urine pregnancy test results during the study will be presented in the individual subject data listings.

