#### **7.17.4 Electrocardiograms**

Shift tables will be presented that summarize the overall ECG interpretation as normal, abnormal not clinically significant, or abnormal clinically significant from baseline to each post-baseline time point.

Individual ECG data will be listed.

A separate statistical analysis plan will be prepared for the Holter monitoring data following an Early Precision QT (EPQT) analysis. This is not included within this statistical analysis plan.

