| Section 14.3.2 | Listings of Deaths, Other Serious and Certain Significant Adverse Events                                                               |
| Table 14.3.2.1        | Listing of Deaths (Safety Population)                                                                                                         |
| Table 14.3.2.2        | Listing of Serious Adverse Events (Safety Population)                                                                                         |
| Table 14.3.2.3        | Listing of Adverse Events Resulting in Discontinuation of Study (Safety Population)                                                           |
| Section 14.3.4 | Abnormal Laboratory Value Listing                                                                                                      |
| Table 14.3.4          | Listing of Abnormal Laboratory Results (Safety Population)                                                                                    |
| Section 14.3.5 | Additional Safety Data Summaries                                                                                                       |
| Table 14.3.5.1        | Summary Statistics of Absolute and Change from Baseline for Clinical Laboratory Parameters (Safety Population)
Note: continuous tests only |
| Table 14.3.5.2        | Shift Table for Clinical Laboratory Parameters (Safety Population)                                                                            |
| Table 14.3.5.3        | Summary Statistics of Absolute and Change from Baseline for Vital Signs (Safety Population)                                                   |
| Table 14.3.5.4        | Shift Table for Electrocardiogram Interpretations (Safety Population)                                                                         |
| Table 14.3.5.5        | Summary Statistics of Absolute and Change from Baseline in Scale for the Assessment and Rating of Ataxia (SARA) (Safety Population)           |

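### The SAP does not say whether unscheduled and repeat results count towards the worst post-baseline laboratory shift, and read literally its general rule leaves them out

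*SAP*

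**What the plan says.** SAP 7.1 (General) sets the rule for off-schedule data: "For safety summaries, the unscheduled and repeat assessments will not be included in descriptive statistics". Such results go to the listings instead. The same section lets an unscheduled assessment serve as baseline if it is the last one before dosing.

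SAP 7.17.2 plans the laboratory shift table in one sentence: "Shift from baseline to worst post-baseline laboratory findings based on normal range criteria will also be summarized". It does not say which post-dose records are eligible. Section 9 lists the output as Table 14.3.5.2, "Shift Table for Clinical Laboratory Parameters (Safety Population)", among the additional safety data summaries, again without a selection rule.

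Protocol 8.4.3 describes the same table: "Shifts based on normal ranges between the baseline and the worst on-study value will be tabulated by dose level and treatment group". It sets no limit to scheduled visits. Protocol 2.3.7 explains why off-schedule draws exist: "Unscheduled safety laboratory assessments may be obtained at any time during the study to assess potential safety concerns". Protocol 5.4 also allows unscheduled visits to repeat laboratory tests.

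SAP Section 4 declares its analyses consistent with the protocol and records no departure on this point.

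**The concern.** By-visit means and a worst-value shift need different records. Leaving off-schedule results out of by-visit means is sensible, because those results belong to no nominal visit. A worst-value shift is taken over the whole post-dose period, so each valid result in that period is a natural candidate. SAP 7.1 applies one exclusion to safety summaries and does not separate the two uses.

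The draws in question include those ordered because something may be wrong. If they are excluded, a subject whose only out-of-range result came from such a draw is tabulated as staying within range. There is also an asymmetry: an unscheduled result before dosing can set the start of a shift, but on the broad reading one after dosing cannot set its end.

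Change in safety laboratory results is part of the primary endpoint. Table 14.3.5.1 is restricted to continuous tests, so for any other laboratory test the shift table is the only listed laboratory summary that could carry it.

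**Working it through.** There is no stated figure to reproduce: the study has no formal sample-size calculation and no safety test. The check compares the texts and then sizes the effect.

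**1. Two readings of SAP 7.1**

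- *Broad.* The shift table is a safety summary, the exclusion has no exception, and SAP 7.1 contrasts descriptive statistics with listings. The documents also apply descriptive wording to categorical data: AE frequencies in the protocol synopsis, the proportion receiving each dose level in protocol 8.4.3, and sex, race and ethnicity in SAP 7.11. On this reading the table uses scheduled draws only.
- *Narrow.* Descriptive statistics means by-visit summaries, as in protocol 8.1: "Descriptive statistics by dose level and treatment group will be tabulated by visit". SAP 7.17.2 attaches the term to observed and change values at each visit or timepoint. On this reading the shift table is unaffected.
- *What the SAP could have said.* SAP 7.2 has the narrower term available: "For all variables, only the observed data from the subjects will be used in the by-visit summaries". SAP 7.1 does not use it.
- *Contrast with ECG.* ECG shifts in SAP 7.17.4 run to "abnormal clinically significant from baseline to each post-baseline time point", so a visit-level exclusion fits them. The laboratory shift has no timepoint, so its eligible records are left undefined.

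**2. When the readings give different tables**

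A subject's category changes only if an off-schedule post-dose result is out of range and every scheduled post-dose result for that test is in range in that direction. A repeat that confirms an out-of-range scheduled result changes nothing in that direction, because the scheduled result already counts.

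**3. Effect of one omitted subject**

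Inputs (SAP 3.1): 6 active and 2 placebo subjects in each of 4 cohorts, giving 4 × 6 = 24 active and 4 × 2 = 8 placebo. The effect on a proportion is 1/n.

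| Group | n | Effect of one subject |
|---|---|---|
| One dose level | 6 | 1/6 = 16.7 points |
| Pooled RGLS8429 | 24 | 1/24 = 4.2 points |
| Pooled placebo | 8 | 1/8 = 12.5 points |

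The pooled active-minus-placebo difference moves by −1/24 = −4.2 points if the omitted subject is on active, and by +1/8 = +12.5 points if on placebo. The count within an arm can only be too low, but the comparison can be biased either way.

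**4. Where only an off-schedule draw could record a transient change**

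Scheduled post-dose draws, from protocol 5.2 to 5.3.4:

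| Panel | Draws | Number | Longest gap |
|---|---|---|---|
| Hematology, chemistry, urinalysis | Days 2, 8, 15, 22, 29 | 5 | 7 days |
| Lipids | Days 2, 15, 29 | 3 | 29 − 15 = 14 days |
| Coagulation | 4 hr, 24 hr (Day 2), Day 29 | 3 | 29 − 2 = 27 days |

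**5. Illustration with an assumed frequency**

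Let q be the chance that a subject's worst value appears only off schedule, with subjects independent. The documents give no value for q. The chance of at least one misclassified subject is 1 − (1 − q)^n.

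| Assumed q | n = 6 | n = 8 | n = 24 |
|---|---|---|---|
| 2% | 11.4% | 14.9% | 38.4% |
| 5% | 26.5% | 33.7% | 70.8% |
| 10% | 46.9% | 57.0% | 92.0% |

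These values show only how the result depends on q. They do not estimate it.

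**The case against.** The narrow reading has real support. SAP 7.1 treats continuous variables and categorical counts separately, and a shift table is categorical. SAP 7.17.2 puts the shift in its own sentence, without the term descriptive statistics. Protocol 8.1 itemises those statistics for continuous endpoints. The SAP's claim of consistency with the protocol also favours the reading that avoids a conflict. The protocol does not name unscheduled results, so their inclusion is inferred from its unrestricted wording. This all stands, and it makes the point an ambiguity rather than a proven contradiction. It does not settle the matter, because the documents do not keep to that usage and SAP 7.1 states its exclusion without qualification.

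The practical effect is also limited. Confirmatory repeats drop out, no formal test uses the table, and dose escalation rests on blinded review of AEs and laboratory data. All results are listed, out-of-range values appear in Table 14.3.4, and clinically significant abnormalities become AEs under protocol 9.3. The 1/n figures are simply the weight of one subject. These points limit the severity. They leave a gap, though: an out-of-range result that meets no AE criterion would appear only in listings and be missing from the table meant to count it.

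Finally, scheduled-only selection is a possible convention, because subjects tested more often have more chances of an abnormal value. That is a fair argument, but a plan that adopts the convention should say so and record it as a departure from the protocol's wording.

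**Conclusion.** The concern holds. The SAP does not define which records enter the worst post-baseline laboratory shift. Applied literally, its general exclusion can drop a subject's true worst value, contrary to the plain meaning of the protocol's worst on-study value. Any departure from the protocol depends on the broad reading; the silence on eligible records does not.

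Each affected subject shifts a dose-group proportion by 16.7 points, or the pooled difference by −4.2 or +12.5 points. These figures assume full cohorts of 6 and 2. Frequency is unknown. Because the results remain in the listings, this should be fixed but does not threaten the trial.

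**What to change.** Three text changes:

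- **SAP 7.1:** limit the exclusion of unscheduled and repeat assessments to by-visit and by-timepoint descriptive statistics.
- **SAP 7.17.2:** add that the worst post-baseline value in shift tables is selected from all valid post-dose results, whether scheduled, unscheduled or repeat. Add that results from samples documented as invalid and replaced by a repeat are not used. The SAP should say what documentation makes a sample invalid.
- **Table 14.3.5.2:** footnote this rule.

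If scheduled-only selection is what the sponsor intends, SAP 7.17.2 should say so and SAP Section 4 should record the departure from protocol 8.4.3.

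The cost is a few words in SAP 7.1, two sentences in SAP 7.17.2 with the invalid-sample criterion, one footnote and a record-selection flag in programming. No new data are needed.

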### 7.2 Handling of Dropouts or Missing Data

There will be no imputations for missing data other than that implicit by ignoring missing data when using the trapezoidal rule for the calculation of AUCs. For all variables, only the observed data from the subjects will be used in the by-visit summaries.

The following imputation dates for AE and concomitant medication will only be applied for determination of TEAEs and prior/concomitant medication.

### **7.2.1 Handling of missing/ incomplete dates for Adverse Event**

**Imputation rules for missing or partial AE start date are defined below:**

a) If only Day of AE start date is missing:

If the start date has month and year but day is missing, the first day of the month will be imputed.

- If this date is earlier than the first dose date, then the first dose date will be used instead.
- If this date is later than the stop date (possibly imputed), then the stop date will be used instead.

b) If Day and Month of AE start date are missing:

If the start date has year, but day and month are missing, the 1st of January will be imputed.

- If this date is earlier than the first dose date, then the first dose date will be used instead.
- If this date is later than the stop date (possibly imputed), then the stop date will be used instead.

c) If Year of AE start date is missing:

If the year of AE start is missing or AE start date is completely missing then imputation will not be done and this AE will be considered as TEAE.

### **7.2.2 Handling missing or partial Prior/Concomitant Medication Dates**

**Missing or partial medication start date:**

- a) If only Day is missing, the first day of the month will be assumed.
- b) If Day and Month are both missing, the first day of the year will be assumed.
- c) If Day, Month and Year are all missing, the day before the first dose date will be assumed.

**Missing or partial medication stop date:**

- a) If only Day is missing, the last day of the month will be assumed.
- b) If Day and Month are both missing, the last day of the year will be assumed.
- c) If Day, Month and year are all missing, ‘continuing’ status to stop date will be assigned.

## **7.3 Multiple Comparisons and Multiplicity**

There will be no multiple comparison adjustment for various analyses.

No formal statistical tests will be conducted to assess the safety or tolerability of RGLS8429.

## **7.4 Adjustments for covariates**

Not applicable.

## 7.5 Multicenter Studies

This is a single-center study.

## 7.6 Examination of Subgroups

No subgroup analyses are planned.

## 7.7 Coding dictionaries

Medical history, AEs and medical procedures will be coded using the Medical Dictionary for Regulatory Activities (MedDRA, Version 24.0 or higher). Medications will be coded using the World Health Organization dictionary of medical codes (WHO Global B3 format - March 2021).

## 7.8 Analysis Populations

### 7.8.1 Screened Population

Screened population includes all subjects who signed the informed consent form

### 7.8.2 Randomized Population

Randomized population includes all subjects who are randomized into the study.

